## **1. BACKGROUND INFORMATION**

Non-invasive treatment options are in high demand by patients wanting to improve their appearance without surgical intervention. As a result, patients now have a variety of options for non-invasive skin rejuvenation, from laser and light-based treatments to devices that utilize ultrasound and radiofrequency, however this was not always the case. Initial skin rejuvenation procedures utilized ablative lasers, such as the carbon dioxide (CO2) and erbium:yttrium-aluminum-garnet (Er:YAG), and resulted in substantial improvement in skin appearance, texture, rhytides and laxity[1-3]. However, since ablative treatments destroy the epidermal layer of the skin in order to penetrate and heat the deeper dermal layers, ample post-procedure recovery time is required and patients may experience side effects lasting for a few weeks. Furthermore, hypo- or hyperpigmentation, prolonged wound healing and even scarring can occur following ablative procedures [4-6]. Treatment methods with less risk of side effects and post-treatment down time are in high demand. As such, the choices are vast and varied, ranging from fractional non-ablative laser devices to those that use radiofrequency [7-15]. Fractional lasers inflict microscopic zones of thermal damage in the dermal layers of the skin without destruction of the epidermis, thereby reducing recovery time significantly as compared to ablative procedures[16]. Treatment with non-fractional, non-ablative laser devices requires little to no post-procedure recovery time. Nonablative lasers of various wavelengths are effective for skin rejuvenation based on the principle of selective photothermolysis, whereby laser light is absorbed by hemoglobin in blood vessels and melanin in pigment-producing skin cells [17, 18]. Absorption of laser light by these molecular chromophores results in the production of heat, leading to destruction of unwanted blood vessels and pigment cells. Heat production within the dermis by the laser light also results in immediate collagen contraction and heat-induced wound healing that, over time, causes a cascade of cellular events leading to new collagen production and improved skin appearance [8, 10, 19-23].

[REDACTED]

[REDACTED]

## **2. [REDACTED]**

[REDACTED]

[REDACTED]

### **3. STUDY OBJECTIVES**

The objectives of this pivotal study are:

- a. To evaluate the safety of the Cutera excel V laser and the Micro-Lens Array attachment.
- b. To evaluate the efficacy of the Cutera excel V laser and the Micro-Lens Array attachment in the improvement of skin quality.

### **4. STUDY DESIGN**

This is an open-label, prospective, study in approximately 60 male or female subjects, age 18 to 65 years who desire laser treatment for the improvement of rhytides, lentigines, pigmentation, erythema, telangiectasia, pore size and skin texture. [REDACTED]

[REDACTED]. Subjects will receive [REDACTED] laser treatments, [REDACTED]. Subjects will be contacted by phone 7 days [REDACTED] after their first treatment for follow-up. Subjects will return to the site after final study treatment for two follow-up visits: 6 and 12 weeks [REDACTED]).

#### **4.1 Study Endpoints**

##### **4.1.1 [REDACTED] Safety Endpoint**

Safety of the Cutera excel V laser and the Micro-Lens Array attachment assessed by the frequency and severity of device related adverse events.

##### **4.1.2 [REDACTED] Efficacy Endpoints**

- Efficacy of treatment(s) with Cutera excel V laser and the Micro-Lens Array attachment as assessed by the study investigator from the 2nd treatment onward for the improvement of skin quality.
- Subject satisfaction levels as assessed from the subject questionnaire.

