### 4.3 Study Effectiveness Assessments

#### 4.3.1 Investigator Assessments

At baseline, and starting after the second treatment, the Investigator will assess the efficacy of the Cutera excel V laser with the MLA attachment treatment using the GAIS, [redacted]  
[redacted] Baseline photos of subjects may be used while assessing the GAIS, [redacted]  
[redacted]

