#### Global Aesthetic Improvement Scale (GAIS): [Only performed after treatment]

[figure not shown]
4 = Very Significant Improvement [redacted]

3 = Significant Improvement [redacted]

[figure not shown]
2 = Moderate Improvement [redacted]

1 = Mild Improvement [redacted]

0 = No Change [redacted]

[Redacted text]

[Redacted text]

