#### 4.4.3 [REDACTED]

#### 4.5 Photographs

Standardized digital photographs will be taken of each subject's treatment area at baseline, prior to and post all laser treatments and at each follow-up visit. Treatment area will be cleansed and any jewelry and make-up will be removed from the area being photographed. For facial photographs, hair will be pulled away from the face with a headband.

Facial photographs will be obtained from at least 3 angles: with the subject facing forward, 45° to the right and 45° to the left. Photographs will be taken in the same windowless room equipped with adequate lighting. The room lighting, camera positioning and subject positioning should be consistent for all study visit photographs. Digital camera settings should remain the same for all photographs and the highest resolution settings should be utilized.

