### 5. STUDY POPULATION

#### 5.1 Study Subject Recruitment and Selection

Approximately 60 male or female subjects, ages 18 to 65, with Fitzpatrick Skin Type I-VI who desire laser treatment for rhytides, lentigines, pigmentation, pore size, acne scars, erythema, telangiectasia and skin texture. Subjects will be recruited to participate from the local population. Subjects may also be recruited from the Investigator's existing patient database or from patients who present themselves to the study site requesting treatment. Only subjects who meet all eligibility criteria and who provide written informed consent will be enrolled into the study.

Each subject will be evaluated by the Investigator to assess his/her suitability for entry into the study according to the following inclusion and exclusion criteria.

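### The investigator-rated efficacy endpoint (secondary) is scored open-label by a rater who knows which state is post-treatment; an order-masked rating of the photographs already required would reduce this bias

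*Combined protocol and SAP*

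**What the plan says.** Section 4 describes the design: "This is an open-label, prospective, study in approximately 60 male or female subjects". No control group appears in the legible text. Section 3 calls the study pivotal and gives two objectives, safety and efficacy in improving skin quality.

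Section 4.1.2 lists two efficacy endpoints. The first is efficacy "as assessed by the study investigator from the 2 nd treatment onward for the improvement of skin quality". The second is "Subject satisfaction levels as assessed from the subject questionnaire". The table of contents ranks both as secondary and safety as primary.

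Under section 4.3.1, "the Investigator will assess the efficacy of the Cutera excel V laser with the MLA attachment treatment using the GAIS"; further instruments are redacted. The investigator may consult baseline photographs while scoring. The GAIS heading adds "Only performed after treatment", and its legible grades run from 0 (no change) up to 4.

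Section 4.5 requires standardised photographs at baseline, around every treatment and at each follow-up visit: "The room lighting, camera positioning and subject positioning should be consistent for all study visit photographs". No legible text asks for these to be read with the order masked.

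**The concern.** The rater treats the subject, knows that treatment has been given, and scores improvement at a time when improvement is expected. Any photograph consulted is already identified as the baseline one. Nothing in the legible endpoint makes errors of expectation cancel. On the grades shown, a subject who has not changed can be misjudged only upward (a grade for worsening may be redacted).

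The efficacy objective is at stake. With no comparator in the legible text, the reported improvement contains whatever the device did plus whatever the rater expected, and the endpoint gives no means of telling the two apart. The material for a masked rating is already being collected, so much of this exposure is avoidable.

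**Working it through.** **The plan's own figure.** The only figure is the sample size of about 60 (sections 4 and 5.1). Its derivation in section 10.1 is not legible, so it cannot be reproduced. The point does not depend on it.

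**Step 1: what expectation alone can produce.** Assume no device effect, and that expectation leads the rater to score a share q of 60 subjects at 1 or more. The documents give no value for q, so a range is shown. Reported improved = 60 × q.

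| Assumed q | Reported improved | Exact 95% CI |
|---|---|---|
| 20% | 12 of 60 | 10.8% to 32.3% |
| 40% | 24 of 60 | 27.6% to 53.5% |
| 60% | 36 of 60 | 46.5% to 72.4% |

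The intervals measure sampling error and do not reveal the bias: a truth of zero lies outside all three.

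**Step 2: what masking the order does.** Show each subject's baseline and follow-up photographs as A and B in random order. If there is no change and the rater cannot tell the order, the follow-up photograph is chosen with probability 0.5. Let the rater's grade for the perceived difference be g, signed + if follow-up was chosen and − if baseline was chosen. Its expectation is 0.5 × g + 0.5 × (−g) = 0, however large a difference the rater tends to see.

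The sign is essential. Suppose the rater may also answer no difference, and sees a difference in 12, 24 or 36 of 60 unchanged subjects. Half of those picks fall on follow-up: 6, 12 or 18. Counting them as improved and all other subjects as not improved would still report 10%, 20% or 30% improved. Only follow-up picks minus baseline picks (6 − 6, 12 − 12, 18 − 18) has expectation zero.

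**Step 3: operating characteristics, forced choice.** Let X be the number of follow-up picks. With no change, X is Binomial(60, 0.5). At an assumed one-sided level of 0.025, the smallest qualifying count is 39: P(X ≥ 39) = 0.0137.

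| True follow-up pick rate | Power, at least 39 of 60 |
|---|---|
| 0.60 | 0.26 |
| 0.65 | 0.56 |
| 0.70 | 0.84 |
| 0.75 | 0.97 |
| 0.80 | 0.998 |

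With 54 evaluable pairs the rule is at least 35 (level 0.020, power 0.84 at 0.70). With 48 it is at least 32 (level 0.015, power 0.75 at 0.70).

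**Step 4: if no difference is allowed.** The 39-of-60 rule no longer applies, because only non-tied pairs carry information. With 24 such pairs, P(X ≥ 18) = (134,596 + 42,504 + 10,626 + 2,024 + 276 + 24 + 1) / 2^24 = 190,051 / 16,777,216 = 0.011. At 17 the probability is 0.032, so 18 is the smallest count that meets 0.025.

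**The case against.** **Redaction.** Section 4.1.3, parts of 4.3 and all of section 10 are not legible. Section 4.3.1 has an assessment at baseline although the GAIS is scored only after treatment, so another instrument must exist in the redacted text. A masked review may exist there too. This stands: the point is limited to the endpoint as legible in 4.1.2. A reader might infer that the trial has no masked reading at all; the documents do not show that.

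**Rank.** Efficacy is secondary, and the safety endpoint is not touched. This stands and limits the weight of the point, although efficacy is one of only two stated objectives.

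**Masking is incomplete.** An investigator who has treated and photographed a subject repeatedly may recognise some pairs. Recognition weakens the symmetry in step 2, but leaves those pairs no worse placed than under the present, wholly unmasked rating.

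**Other sources of change.** Inclusion criterion 5 requires very limited sun exposure and daily sunscreen throughout. A masked rater would still prefer the follow-up photograph if those measures, or natural change, improved the skin. This stands. A reader might infer that masking would make the efficacy objective fully answerable, or that without it the objective cannot be addressed at all. Neither follows: the absence of a comparator is a separate limit that masking leaves in place.

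**Size.** A reader might also infer that an inert device would show most subjects improved. That happens only at the assumed 60% rate; 12 and 24 of 60 are not majorities.

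**Conclusion.** The concern holds in limited form. The investigator-rated endpoint in 4.1.2 is an open-label rating made with knowledge of which state is post-treatment, so rater expectation can add apparent improvement that the endpoint cannot separate from device effect. The size is unknown. The 12, 24 or 36 of 60 rest on assumed expectation rates of 20%, 40% and 60%. The operating characteristics of the masked rating rest on an assumed one-sided level of 0.025, the stated numbers of evaluable pairs, and a rater who does not recognise the order. The change is worth making, but it affects a secondary endpoint and reduces one source of bias only. The subject-satisfaction endpoint remains open-label.

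**What to change.** If a masked review already exists in the redacted sections, refer to it in 4.1.2 and state which result carries the efficacy conclusion. If not, amend 4.1.2 and 4.3.1 as follows:

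1. Keep the live GAIS from the second treatment onward as supportive.
2. For baseline versus the 6-week and 12-week visits, the sponsor strips dates and presents each subject's pair as A/B in random order.
3. The same site investigator must choose the photograph that looks better and grade the difference.
4. After unmasking, sign the grade: + if follow-up was chosen, − if baseline was chosen.
5. Report the mean signed grade and the proportion of follow-up picks against 50%, and rest the efficacy conclusion on these. State beforehand which of the two visits carries it.
6. If no difference is to be a permitted answer, test only the non-tied pairs and report follow-up minus baseline picks.

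The cost is protocol wording, sponsor time to code about 60 pairs per follow-up visit, and a short rating session per site. No extra reader, visit or procedure is needed. The downsides are that photographs show texture less well than live inspection, the treating investigator may recognise some pairs, and the reported improvement may be lower. The report should also say that natural change and the effect of sun avoidance and sunscreen remain.

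### Section 4.3.1 makes the baseline photographs optional when the investigator scores the GAIS, so ratings of change can rest on memory for some subjects and on photographs for others

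*Combined protocol and SAP*

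**What the plan says.** Section 4.3.1 has the investigator assess efficacy with the GAIS, and possibly with other scales, because the text after the scale's name is blacked out. On the reference for the rating it says: "Baseline photos of subjects may be used while assessing the GAIS". The readable scale runs from 0 (no change) to 4 (very significant improvement).

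Section 4.5 requires standardised photographs at baseline, before and after every laser treatment, and at each follow-up visit, with room lighting, positioning and camera settings held constant. Section 4 describes an open-label study of about 60 subjects with "two follow-up visits: 6 and 12 weeks" after the final treatment. Section 4.2 puts each subject's participation at about 14 months.

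Three places bear on when the rating is made:

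- Section 4.1.2, without naming the GAIS, sets investigator-assessed efficacy from the second "treatment onward for the improvement of skin quality".
- Section 4.3.1 says "At baseline, and starting after the second treatment".
- The heading of the scale says "Only performed after treatment".

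The contents list labels the efficacy endpoints secondary and the safety endpoint primary. Section 3 calls the study pivotal and makes efficacy one of its two objectives.

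**The concern.** A GAIS score has no meaning without a picture of the skin before treatment. If the rater may choose whether to look at that picture, the reference can differ between subjects, between visits in one subject and, if there is more than one investigator, between investigators. Two subjects with the same true change could then receive different scores because one was compared with a photograph and the other with a recollection. A rater who knows the subject was treated may also recall the starting state as worse than it was.

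At stake is how the investigator-rated efficacy result can be read. The point does not touch the safety endpoint.

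**Working it through.** The plan states no figure on this point, so the check sets the passages side by side. A count of rating occasions is used only for the lesser timing point.

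**Reference for the rating**

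1. *What the scale needs.* Each score from 0 to 4 compares present skin with baseline skin, so every rating needs a baseline reference.
2. *What the plan supplies.* Section 4.5 makes standardised baseline photographs compulsory. A reference therefore exists for every enrolled subject at every rating.
3. *What the rule demands.* Section 4.3.1 permits use of that reference and does not require it. No readable passage asks for a record of whether it was used, so photograph-based and memory-based ratings could not be told apart afterwards.
4. *How long memory would have to serve.* Participation lasts about 14 months, and the last follow-up visit is 12 weeks after the final treatment, near the end of that period. The interval back to baseline is longest for the ratings made after the full course.
5. *Who rates.* The investigator, in an open-label study. A photograph does not remove knowledge of treatment, but it fixes what the skin is compared with.

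Steps 2 and 3 together give the finding: the plan collects the reference and then leaves its use to choice.

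**Timing of the first rating (lesser point)**

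Let *t* be the number of laser treatments. It is blacked out in the body. The contents list refers to treatments 1 to 6. Section 4.2 allows up to 9 visits and lists the phone contact among them:

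- phone contact counted: 1 + 1 + *t* + 2 = 9, so *t* = 5;
- phone contact not counted: 1 + *t* + 2 = 9, so *t* = 6.

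Possible GAIS occasions per subject, including the two follow-up visits:

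- from the second-treatment visit onward: (*t* − 1) + 2, which is 7 for *t* = 6 and 6 for *t* = 5;
- only at visits after the second-treatment visit: (*t* − 2) + 2, which is 6 for *t* = 6 and 5 for *t* = 5.

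The two readings differ by one rating per subject. The word baseline in section 4.3.1, applied literally to the GAIS, would add a rating that a change scale cannot give. The scale's own heading appears to exclude it.

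**The case against.** **Against the main point.** Baseline photographs are compulsory, standardised and open to the rater, and an experienced investigator will usually look at them, so it would be unfair to assume that ratings are made from memory. Text after the sentence in section 4.3.1 is blacked out, and section 6 or Appendix 1 may already make the comparison compulsory. The open-label design remains whatever is done about photographs, and efficacy is secondary. All of this limits the weight of the point. It does not remove it: the readable rule allows ratings without the photographs, and if another section requires them, section 4.3.1 should say the same.

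**Stronger readings a reader might infer, and why the documents do not support them.**

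- *Three conflicting timings.* The three statements can be reconciled. The baseline assessment in section 4.3.1 may belong to blacked-out scales, the heading of the scale can be read as taking the GAIS out of baseline, and the two phrases about the second treatment can mean the same thing.
- *Scoring on freshly treated skin.* The heading's wording naturally means after baseline. The remark in section 1 that heat "also results in immediate collagen contraction" is general background on mechanism and says nothing about when the GAIS is scored.
- *Choosing the best of several ratings.* No readable passage describes such a rule, nor pooling across visits.
- *No analysis time point.* This cannot be asserted while sections 6 and 10 and Appendix 1 are unreadable. A visit named there would fit inside the period in section 4.1.2 without contradicting it.

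**Conclusion.** The point holds as a cheap improvement. In section 4.3.1 the baseline reference for a change scale is optional, although the plan already collects that reference under standardised conditions. As written, GAIS ratings can rest on different references and are open to recall bias.

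Its reach is every GAIS rating in about 60 subjects. Its numerical size cannot be given, because the documents report neither rater agreement nor how often the photographs would go unused. The conclusion assumes that no blacked-out text makes the photographs compulsory. If some text does, what remains is a wording mismatch.

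The timing point is a matter of alignment: at most one rating per subject turns on the wording about the second treatment, plus a literal baseline GAIS that the scale's heading seems to rule out. Whether an analysis visit needs to be added depends on section 10.

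**What to change.** **Main change.** In section 4.3.1, replace *may* with *will*, so that every GAIS rating is made against the subject's standardised baseline photographs from section 4.5. No new visit, photograph or reader is needed. The cost is a little more assessment time per rating, and sites must have the baseline images to hand at each one. Rater knowledge of treatment stays as it is.

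**Secondary change, after checking sections 6 and 10 and Appendix 1.**

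- Use one statement of when the first GAIS rating is made in section 4.1.2, section 4.3.1 and the heading of the scale. If baseline in section 4.3.1 refers only to other scales, say so there.
- If section 10 does not already do so, name one of the two follow-up visits after the final treatment as the efficacy time point and treat earlier ratings as descriptive. Nothing readable favours 6 weeks over 12 or the reverse, so the sponsor should choose and give the reason.

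This part is a change of wording. Its downside is that interim ratings would no longer carry the efficacy conclusion.

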##### **4.1.3 [REDACTED]**

[REDACTED]

#### **4.2 Study Duration**

Subjects enrolled in this trial will participate for approximately 14 months, [REDACTED], [REDACTED], and 2 follow-up visits at 6 and 12 weeks [REDACTED] post final treatment. In

total, enrolled subjects will complete up to 9 visits: 1 screening visit, 1 week phone follow-up after first treatment, up to [redacted] laser treatment visits, and 2 required follow-up visits.

The screening and first laser treatment may be combined into one visit provided that the subject has signed the IRB-approved Informed Consent Form prior to the commencement of any study-related procedures and has met all criteria to be enrolled in the study.

### 4.3 Study Effectiveness Assessments

#### 4.3.1 Investigator Assessments

At baseline, and starting after the second treatment, the Investigator will assess the efficacy of the Cutera excel V laser with the MLA attachment treatment using the GAIS, [redacted]  
[redacted] Baseline photos of subjects may be used while assessing the GAIS, [redacted]  
[redacted]

#### Global Aesthetic Improvement Scale (GAIS): [Only performed after treatment]

[figure not shown]
4 = Very Significant Improvement [redacted]

3 = Significant Improvement [redacted]

[figure not shown]
2 = Moderate Improvement [redacted]

1 = Mild Improvement [redacted]

0 = No Change [redacted]

[Redacted text]

[Redacted text]

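### Does a GAIS with no visible grade below 'No Change' make the investigator-rated improvement positive by construction?

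*Combined protocol and SAP*

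**What the plan says.** Protocol Section 4.1.2 lists two efficacy endpoints. One is the investigator's judgement, from the second "treatment onward for the improvement of skin quality"; the other is subject satisfaction from a questionnaire. It names no summary statistic and no threshold.

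Section 4.3.1 sets the timing: "At baseline, and starting after the second treatment, the Investigator will assess the efficacy". The instrument named is the GAIS, followed by a blacked-out stretch. It adds "Baseline photos of subjects may be used while assessing the GAIS", again followed by a redaction.

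The scale is headed "Global Aesthetic Improvement Scale (GAIS): [Only performed after treatment"]. Its readable rows run from "4 = Very Significant Improvement [redacted"] to "0 = No Change [redacted"]. In all five rows the number and label are readable and the text beside them is blacked out. After the 0 row come two wholly blacked-out blocks.

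On design, Section 4 states: "This is an open-label, prospective, study in approximately 60 male or female subjects". No control arm is described in the readable text. The table of contents lists Section 10.2 on statistical analysis methods, but its text cannot be read in the public version.

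**The concern.** The lowest readable grade is no change. On a scale that truly ends there, errors in the favourable direction raise the score and errors in the other direction disappear into 0. The average is then above zero even when nothing has happened to the skin. GAIS is given only after treatment, so no baseline score can be subtracted, and no visible control arm shows how large the offset is.

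The setting adds weight. The treating side rates its own open-label result, baseline photographs are optional, and the study calls itself pivotal in Section 3. Pigmentation and erythema are among the treatment targets, and these could get worse as well as better. If the concern held, a positive mean GAIS would be guaranteed, and subjects who worsened would not appear in the efficacy result.

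**Working it through.** **1. Plan's own figure.** There is none to reproduce. The readable text gives no SD, effect size, alpha or success threshold for GAIS. The only usable number is the sample size of about 60 (Sections 4 and 5.1).

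**2. Assumed model.** True change is zero and rating error is normal with SD s grades. The rating is rounded to the nearest grade, set to the floor if below it, and capped at 4. The documents do not give s, so a range is used.

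**3. Formulas.**
- Proportion scored improved: P(score ≥ 1) = 1 − Φ(0.5/s).
- Mean with floor 0: sum over k = 1 to 4 of [1 − Φ((k − 0.5)/s)].
- Mean with floor −1: the same sum minus Φ(−0.5/s).

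For s = 0.5, P(score ≥ 1) = 1 − Φ(1) = 0.159. The floor-0 mean is 0.1587 + 0.0013 = 0.160, and the floor −1 mean is 0.1600 − 0.1587 = 0.001.

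**4. Results.** The last column is the share of 20,000 simulated trials of 60 subjects in which a one-sample t-test of mean > 0 rejects at one-sided 2.5%.

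| s | P(score ≥ 1), any floor | Mean, floor 0 | Mean, floor −1 | Rejection, floor 0 |
|---|---|---|---|---|
| 0.25 | 0.023 | 0.023 | 0.000 | 4.7% |
| 0.40 | 0.106 | 0.106 | 0.000 | 89.3% |
| 0.50 | 0.159 | 0.160 | 0.001 | 99.1% |
| 0.75 | 0.252 | 0.276 | 0.023 | 100% |
| 1.00 | 0.309 | 0.382 | 0.073 | 100% |
| 1.25 | 0.345 | 0.485 | 0.140 | 100% |

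**5. What this shows.** The mechanism is real for a mean on a scale that stops at 0, but its size depends on s. Below about a quarter of a grade it nearly vanishes. The proportion improved does not involve the floor at all: at s = 0.5 it is 0.159 with a floor of 0, −1 or −4. Adding a worse grade would leave a responder rate unchanged.

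**6. Setting the model against the plan.** The calculation bears on this trial only if two things are true.
- *The scale has no grade below 0.* The two blacked-out blocks stand directly after the 0 row. They could hold a lower grade, further investigator scales, or the subject satisfaction section that the contents list as 4.3.3. The text does not settle which.
- *GAIS is analysed as a mean against zero.* No readable sentence says so. The rejection rates above belong to a test supplied for this check, not to one found in the plan.

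**7. Other records of worsening.** Section 4.4.1 grades adverse effects after treatment and at each later visit. Section 7.2 requires every adverse sign or symptom that is observed or volunteered to be recorded, however mild or rare. Section 4.5 calls for standardised photographs at baseline, before and after every treatment, and at each follow-up visit.

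**The case for a change.** The best argument for the concern is the redaction pattern. All five rows keep their number and label, and only the descriptor is hidden; blacking out a whole worse row would break that pattern. The hidden blocks also have another natural explanation, since Section 4.3.3 should appear thereabouts and the gap after the GAIS is named suggests further scales. This makes a hidden lower grade less likely. It does not exclude it, and a criticism that depends on what lies under a redaction is not established.

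The arithmetic for a mean also stands under its assumptions. With a true worsening of half a grade, a floor-0 mean would still be positive: 0.023, 0.095 and 0.183 at s = 0.5, 0.75 and 1.0.

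A floor would lose information even where it adds no bias. At s = 0.5 with no true change, a symmetric scale would show 15.9% improved, 15.9% worse and 1 − 2 × 0.159 = 68.2% unchanged. A scale ending at 0 would show 15.9% improved and 84.1% unchanged, hiding the balance that reveals noise. Adverse-event severity in Section 4.4.1 is graded by interference with activity and need for treatment, not by appearance, so it only partly replaces a worse grade.

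One inference fails even if the scale does stop at 0. It does not follow that scores above 0 carry no information. The floor accounts for a mean of at most 0.485 over the whole range tried, so it could not explain a mean near 2, the moderate grade. The lack of a control arm limits interpretation for other reasons, but that is a separate matter.

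**Conclusion.** No error in the plan is shown. The concern needs a scale that ends at 0 and a mean tested against zero. The first lies behind a redaction and the second appears nowhere in the readable text. If both were true, the offset with no real change would be 0.02 to 0.49 grade for a rating-error SD of 0.25 to 1.25, a range that is assumed and not taken from the documents. If GAIS is reported as a responder proportion, the floor contributes nothing.

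It is reasonable to ask the sponsor to confirm the complete scale and how GAIS will be summarised. That is a clarification, not a defect, and recommending a worse grade could mean asking for something the plan already contains.
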